5.3.3 Outliers

In general, no outliers will be removed from analyses. However, if an outlier is identified in the PK analysis sets, an outlier analysis will be performed to determine the outlier effect on study results.

5.3.4 Multicentre Studies

The study will be performed at a single center.

5.4 Disposition and Background Information data

Descriptive summaries for continuous data and for categorical data will be provided in accordance with Section 5.22.

5.4.1 Subject Disposition

Number of subjects screened, screening failures, randomized, randomized and not taken IMP, randomized and taken IMP, completing the study, withdrawals (including withdrawal reason) and number of subjects in each analysis set will be summarized by dose group.

5.4.2 Protocol Deviations

Protocol deviations will be presented in listings.

5.4.3 Demographic and Baseline Characteristics

Demographic and baseline data will be summarized as appropriate depending on the data type (continuous or categorical), dose group and total.

5.4.4 Medical History

Medical coding will be performed by trained personnel at the Consultinc Oy. AEs and medical/surgical history verbatim terms are coded using the medical dictionary of regulatory activities (MedDRA, latest version available at eCRF setup) and will be presented in listings.

5.4.5 Prior and Concomitant Medications

Statistical Analysis Plan
CX842A2107
Version 2.0, 04-Oct-2023
Author:

Prior and concomitant medications will be coded according to the World Health Organization (WHO) drug dictionary classification system (WHODrug).

5.4.6 Treatment Compliance

During residential visits at the clinic (visits 2, 5 and 7), IMP will be administered at the clinic under medical supervision and entered in the eCRF by study personnel. On other days, subjects will self-administer IMP at home and register each intake of study drug in a paper diary. Text reminders to mobile phones will be sent to the subjects each day. At visit 5 (day 14) to the clinic, subjects will be asked to return any unused study drugs and all empty containers. Percent compliance will be calculated for the home administration period as:

% Compliance = 100 × (# tablets dispensed – # of tablets returned) / Expected # of tablets taken

The subjects in each dose level and dose group and their individual doses will be listed.

5.4.7 Subject Discontinuation

Subjects who discontinue the study will be summarized by reason for discontinuation and dose group and total.

5.5 Safety Analyses

No formal analyses will be performed for safety endpoints. Descriptive summaries for continuous and categorical safety data will be provided in accordance with Section 5.2 if not otherwise stated. Complete listings of all subject safety evaluations will be provided to support each summary table.

All presentations will be based on the full analysis set.

5.5.1 Adverse Events

All adverse events (Aes) occurring during this clinical trial will be coded using the Medical Dictionary for Regulatory Activities (MedDRA), latest version available at the time of eCFR setup.

Aes will be tabulated by System Organ Class (SOC) and Preferred Term (PT). Summary tables will include number of subjects reporting the AE and as percentage of number of subjects by dose group and total. Event counts will be tabulated together with the subject counts.

Aes will be counted as follows:

- In summaries of number of subjects experiencing Aes, subjects with more than one AE within a
 particular SOC are counted only once for that SOC. Similarly, subjects with more than one AE
 within a particular PT are counted only once for that PT.
- In summaries of number of subjects experiencing Aes, subjects reporting an AE more than once within that SOC/PT, but with different severities or different relationships, the worst category of severity/relationship will be used.

All Aes will be listed in by-subject data listings including verbatim term, MedDRA coded term, treatment, severity, relationship to IMP and action taken with respect to IMP.

SAEs will be summarized and listed separately.

5.5.2 Laboratory Evaluations

Descriptive summaries for clinical chemistry, hematology, coagulation, and urinalysis including absolute and relative (%) change from their baselines will be presented by dose group.

All laboratory parameters for individual subjects will be listed and subjects with clinically significant (according to the Investigator's criteria) abnormal values (out of normal range reported by the laboratory) will be flagged and listed separately. The categorization of laboratory parameter observations into 'Normal', 'Abnormal (Not Clinically Significant)', or 'Abnormal (Clinically Significant)' will be summarized using shift-tables (baseline category versus the worst observed categorization over time points post-baseline) by dose group.

5.5.3 Concomitant Medications

Concomitant medications will be summarized using WHO Drug preferred names and show number and percentage of subjects per preferred name.

All data will be presented by dose group and summarized overall, as well as presented in listings by dose group and subject.

5.5.4 Physical Examination

Physical examination will be presented as the number and percentage of subjects with Normal, Abnormal (not Clinically Significant) and Abnormal (Clinically Significant) result over time by Body System, dose group and total.

5.5.5 Vital Signs

Vital signs will be summarized by dose group and total. The summary will include absolute and percent change from baseline at each visit.

5.5.6 Electrocardiogram

Summaries of ECG results and change from baseline over time will be presented by dose group and total.

5.6 Pharmacokinetic Analyses

The PK analysis will be performed based on the PK analysis set. All PK analyses will be performed according to the actual treatment and dose received. Actual sampling time points relative to dosing will be used in the calculations. Pre-dose concentration values will be excluded from the NCA and set to 0.

The parameters to be determined in the study are presented in section 4.6. Parameters directly derived from the plasma concentration – time plot are not further described (i.e., C_{max} , C_{min} , t_{max} , C_{trough}), but all other calculations to be performed are described in detail below. Missing sample around the anticipated T_{max} may be flagged as "not accepted" upon decision by the Pharmacokineticist.

Estimation of the terminal elimination rate constant (λ_z)

The terminal elimination rate constant (λ_z) is calculated by log-linear regression of the terminal portion of the plasma concentration time profile. At least three observations will be used to estimate λ_z and the data points used in each estimation are indicated in the individual PK profiles. Data points for calculation of $T_{1/2}$ via λ_z are selected based on visual inspection of log-concentration-time plots of individual profiles and adjusted if needed. Any exclusion of data points in the terminal phase for this estimation should be clearly justified in the PK analysis log.

The adjusted R² should be considered in the selection of samples for calculation of λ_z and preferably exceed a value of 0.8. If λ_z cannot be reliably estimated, because of a low value of R², it will be flagged as "not accepted" and the associated parameters may be reported as "not determined". Use

of λ_z values obtained from data spanning less than three half-lives is permissible on the judgement of the Pharmacokineticist.

For subjects with insufficient PK data available leading to an extrapolated AUC (AUC_{extrap%}) exceeding 20%, the parameters depending on λ_z will not be reported. The % of extrapolated AUC will be presented for all subjects.

Area under the plasma concentration-time curves (AUCs)

The area under the plasma concentration-time curves (AUCs) are calculated using the linear up -log down method (i.e., linear trapezoidal rule is used when concentration data is increasing and the logarithmic trapezoidal rule is used when concentration data is decreasing) using uniform weighing.

 AUC_{inf} is calculated based on the AUC_{0-t} (AUC from time of dosing to the time point of the last quantifiable plasma concentration) and then extrapolated to infinity using the concentration in the last quantifiable sample (C_{last}) and the estimated terminal elimination rate constant (λ_z), as follows:

 $AUC_{inf} = AUC_{0-t} + (C_{last}/\lambda_z)$

Accumulation ratio (R_{acc})

Accumulation index will be calculated for the observed accumulation ratio:

R_{acc} AUC = AUC_{tau} last dose / AUC_{tau} first dose

R_{acc} C_{max} = C_{max} last dose / C_{max} first dose

terminal half-life (T_{1/2}) The half-life is calculated by ln2/ λ_z .

```
Apparent total clearance (CL/F)
```

Total body clearance for extravascular administration, CL/F= Dose/AUC_{inf}, or CL/F= Dose/AUC_{tau} at steady state

Apparent volume of distribution (V/F)

Volume of distribution based on the terminal elimination phase, V/F =Dose/(λz^*AUC_{inf}), or V/F=Dose/(λz^*AUC_{tau}) at steady state

Average concentration during a dosing interval (C_{aver}) C_{aver} will be calculated for repeated dosing, as follows: $C_{aver} = AUC_{tau}/_{tau}$

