4.6.1 Exploratory analyses

5. Analysis Methods

All statistical analyses will be performed using SAS[®] (Version 9.4 or higher, SAS Institute Inc., Cary, NC, USA).

All PK analyses will be performed on individual plasma concentration-time data by noncompartmental analysis (NCA) using the software Phoenix WinNonlin[®] 8.3 or higher (Certara Inc, Princeton NJ, United States).

All statistical and PK analyses will be performed after this SAP is finalized and approved, the Clean File Report including decisions on analysis sets has been signed, and the database has been locked.

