5.3.2 PK drug concentration data

Concentration results that are below the lower limit of quantification (LLOQ) will be identified as below limit of quantification or not quantifiable (NQ) by the Bioanalysis lab.

For the PK analysis and plots of data, values <LLOQ before the first observed concentration will be entered as zero and values <LLOQ at any other time point will be excluded from the analysis (i.e., handled as missing data). The handling of these values will be justified and documented. Not quantifiable samples will be treated as missing data. In plots, the method used for handling values <LLOQ will be described in a footnote.

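### The pre-dose zero rule in SAP 5.6 is not limited to the first dose, so as written it puts a false 0 at time 0 of Day 14 steady-state profiles

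*SAP*

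**What the plan says.** Section 5.6 opens with rules for all PK analyses. One of them is "Pre-dose concentration values will be excluded from the NCA and set to 0". It has no limit by day, dose or analyte.

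The same section then defines repeated-dose quantities:

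- accumulation: "R_{acc} AUC = AUC_{tau} last dose / AUC_{tau} first dose";
- average concentration, which "will be calculated for repeated dosing, as follows", as AUC_tau divided by tau;
- clearance: "CL/F= Dose/AUC_{tau} at steady state", with V/F built the same way.

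C_max, C_min, t_max and C_trough are set apart: "Parameters directly derived from the plasma concentration – time plot are not further described". The opening of section 5, however, puts all PK analyses under non-compartmental analysis.

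Section 5.3.2 has its own zero rule, limited to unquantifiable values: "values <LLOQ before the first observed concentration will be entered as zero". Two sentences later it adds: "Not quantifiable samples will be treated as missing data".

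C_trough is described in two ways. The abbreviation list places it where a dosing interval begins. Sections 2.4 and 4.6.1 place it where the interval ends, ahead of the following dose.

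**The concern.** A zero before the very first dose is right for a subject who has not yet had the drug. It is wrong on Day 14, when the pre-dose sample follows 13 days of QD or BID dosing and may hold a substantial concentration. Section 5.3.2 does not help, because it covers only values below the LLOQ, and the Day 14 value at issue is quantifiable.

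Two consequences have to be kept apart.

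- **Follows if the zero is used as the time-0 value.** The first trapezoid of the Day 14 profile shrinks. AUC_tau, and with it AUC_0-12 or AUC_0-24, C_aver and R_acc for AUC, fall. Steady-state CL/F and V/F rise. The partial AUCs and C_aver are primary endpoints. R_acc for C_max does not change.
- **Follows only if the zero also reaches the directly read parameters.** Day 14 C_min becomes 0, and so does C_trough (a primary endpoint) under the abbreviation-list wording. The geometric mean and geometric CV% that section 5.2.2 requires for both could not be computed, and the Day 14 plot of HTR against C_min in section 5.7.1 would carry no information.

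**Working it through.** The SAP gives no figure to reproduce. The check has a textual part and an illustration of size.

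**Text.** The pre-dose sentence is general. The formulas after it in 5.6 include last-dose and steady-state quantities. No section exempts Day 14.

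**Formula.** The SAP uses the linear rule while concentrations rise and the log rule while they fall. For a first interval of length t1 that rises from C0 to C1:

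- with the measured C0: t1 × (C0 + C1)/2
- with 0 in its place: t1 × C1/2
- loss: 0.5 × t1 × C0

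The Day 1 denominator of R_acc is unaffected, since 0 is correct there. R_acc for AUC therefore falls by the same proportion as Day 14 AUC_tau.

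**Assumptions.** The SAP states no kinetics and leaves sampling times to the protocol. I assumed a one-compartment oral model at steady state for one generic analyte.

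- Half-life: 3, 6, 9, 12 h
- ka: 0.5, 1.0, 1.5 per h
- First post-dose sample: 0.25, 0.5, 1 h
- Later samples at 1, 1.5, 2, 3, 4, 6, 8, 10, 12, 16, 24 h as applicable
- tau: 12 h (BID) or 24 h (QD)

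This gives 4 × 3 × 3 = 36 scenarios per regimen.

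**Worked example** (half-life 12 h, ka 1 per h, t1 = 1 h, arbitrary concentration units):

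| | BID | QD |
|---|---|---|
| Measured C0 | 1.061 | 0.354 |
| Loss = 0.5 × 1 × C0 | 0.53 | 0.18 |
| AUC_tau, measured C0 | 17.24 | 17.24 |
| AUC_tau, C0 = 0 | 16.71 | 17.06 |
| Change in AUC_tau | −3.1% | −1.0% |
| R_acc AUC | 2.141 → 2.075 | 1.363 → 1.349 |
| CL/F | +3.2% | +1.0% |

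**All 36 scenarios per regimen:**

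| | BID | QD |
|---|---|---|
| True C0 as share of C_max | 10–68% | 0.6–36% |
| Loss in AUC_tau, C_aver, R_acc AUC | 0.23–3.27%, median 1.07% | 0.01–1.09%, median 0.25% |
| Rise in CL/F and V/F | 0.23–3.38% | 0.01–1.10% |
| Ordinary trapezoid error with true C0 | 0.19–2.70%, median 0.44% | 0.20–2.71%, median 0.46% |
| Scenarios where the loss exceeds that error | 27 of 36 | 13 of 36 |
| Median R_acc AUC | 1.604 → 1.579 | 1.144 → 1.140 |

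**Sensitivity to the first sample.** For BID the loss is 0.2–0.8% with t1 = 0.25 h and 0.9–3.3% with t1 = 1 h. In a separate grid (ka 1 per h; half-life 4, 8, 12 h) with t1 = 2 h, it reaches 6.2% for BID and 2.1% for QD.

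**C_trough wording.** The two definitions differ materially only for the first dose. The start-of-interval wording gives 0. The end-of-interval wording gives about 10–75% of C_max (BID) or 0.6–37% (QD) in the same model.

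A Day 14 pre-dose value that is truly below the LLOQ loses nothing under either rule.

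**The case against.** The strongest reply is that the effect is trivial. By these figures the median loss is 1.1% for BID and 0.25% for QD, and for QD it does not exceed ordinary trapezoid error in 23 of 36 scenarios. PK parameters are only summarised, and no test, margin or threshold depends on them. This stands as to size. It does not make the rule correct: the bias runs one way, does not average out over subjects, and is larger for BID than QD.

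Second, the C_min and C_trough consequence goes against the closer text. The sentence confines the zero to the NCA, and the next paragraph separates the parameters read directly from the plot. A zero C_trough further needs the abbreviation entry to prevail over sections 2.4 and 4.6.1. This largely stands, so I treat that branch as an unresolved ambiguity and not as an expected result.

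Third, a value both excluded and set to 0 is open to more than one operation, and only replacement by 0 was quantified here. That is fair, and it is a further reason to rewrite the sentence.

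Fourth, the medians and scenario counts describe the assumed grid, not this trial. That stands; only the direction is free of the assumed kinetics.

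Fifth, 5.3.2 leaves open whether an unquantifiable value is zero or missing. This is a side issue that does not affect quantifiable Day 14 values.

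**Conclusion.** The concern holds. This is a stated rule that gives a wrong result at steady state, not a detail left to the protocol. If the zero is used at time 0, Day 14 AUC_tau, C_aver and R_acc for AUC are biased down and steady-state CL/F and V/F up. The size is about 0.2–3.3% for BID and 0.01–1.1% for QD under the assumed kinetics with a first sample by 1 h, and more if that sample is later. It matters mainly for the BID groups. The loss of C_min and C_trough is conditional on a less natural reading that the SAP does not rule out. The intent was probably the Day 1 sample alone. The point should be fixed because the rule touches primary endpoints and the correction is simple, but it is not a major threat to the trial's conclusions.

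**What to change.** Replace the pre-dose sentence in 5.6 with wording such as:

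> The concentration before the first dose on Day 1 is set to 0 for the NCA and does not count toward C_min. For every later dose, including Day 14, the measured pre-dose concentration is the time-0 value; values below the LLOQ follow section 5.3.2, applied within each profile. C_trough and C_min use measured values, never the substituted zero.

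Align the abbreviation entry for C_trough with sections 2.4 and 4.6.1: the measured sample at the end of the dosing interval (12 h for BID, 24 h for QD), immediately before the next dose where there is one.

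While editing, it would help to make 5.3.2 say plainly whether an unquantifiable value ahead of the first quantifiable one in a profile is zero or missing.

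The cost is one replaced sentence and one abbreviation entry, plus a clause in 5.3.2 if that is taken up. No new data are needed.

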3.1 Study Design

This is a Phase I, single-center, open parallel-group, randomized study designed to evaluate the PK, PD, safety, and tolerability of single and repeated oral doses of linaprazan glurate at three dose levels in healthy male and female subjects.

An overview of the study design is shown in

Figure **1**. The overall schedule of events is presented in Appendix Table 1. The detailed schedule of events for individual visits are tabulated in the CSP (see Tables 8.1-2 to 8.1-7 of the CSP for details).

Subjects will be randomized into 1 of 6 dose groups. There will be 6 dose groups as follows:

- No 1: 25 mg linaprazan glurate (1x25 mg oral tablet) QD for 14 days
- No 2: 50 mg linaprazan glurate (2x25 mg oral tablet) QD for 14 days
- No 3: 75 mg linaprazan glurate (3x25 mg oral tablets) QD for 14 days

- No 4: 25 mg linaprazan glurate (1x25 mg oral tablet) BID for 14 days
- No 5: 50 mg linaprazan glurate (2x25 mg oral tablet) BID for 14 days
- No 6: 75 mg linaprazan glurate (3x25 mg oral tablets) BID for 14 days

Subjects participating in the study will attend 7 visits to the clinical research unit (CRU): a screening visit (Visit 1) followed by 6 visits (Visit 2-7). Visit 2, Visit 5 and Visit 7 are residential stays at the CRU and Visit 3, Visit 4, and Visit 6 are outpatient visits. The participants will also be followed by a remote follow-up/end-of-study visit via telephone (Visit 8), 7 days (±2 days) after the final dose.

Figure 1. Overview of study design

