3.3 Randomization and Blinding

Block randomization (block size=6) stratified by gender will be used to generate the randomization list, which will show the assignment of subjects to 1 of the 6 dose groups given in Section 3.1.

The randomization list of the study was be prepared by a statistician at CRS [name], and transferred to the Trial Master File (TMF) for archiving.

As this is an open label study, the dose group to which each subject is allocated will be recorded in the eCRF. A computer-generated randomization list will be created using SAS Proc Plan, SAS Version 9.4 or later (SAS Institute, Inc., Cary, NC) or equivalent program. The randomization list will contain subject number, block, gender, drug holiday period, and dose group.

The randomization list will be generated and kept by CRS.

No blinding procedures will be followed.

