4.5.5 ECGs

A 12-lead ECG will be recorded pre-IMP administration and at 24 hours post IMP-administration during visits 1, 2, 5 and 7.

The following variables will be recorded:

- Resting Heart Rate (HR)
- PQ/RR
- QRS
- QT
- QTcF

Any abnormalities will be specified and documented as CS or NCS. Abnormal post-IMP findings assessed by the Investigator as CS will be reported as AEs.

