4.6.1 Primary and secondary analyses

PK parameters:

When applicable, the following PK parameters will be obtained or calculated from the plasma concentration-time data of linaprazan glurate and linaprazan after QD or BID dosing with linaprazan glurate:

- AUC_{inf} (the area under the concentration-time curve from time zero extrapolated to infinity)
- AUC_{extrap%} (% extrapolated AUC)
- AUC_{0-t} (area under the concentration-time curve from time zero to t=last)
- Partial AUC (area under the concentration-time curve from time zero to t=12h and 24h, from 12h to 24h, and from 24h to 48h)
- C_{max} (maximum observed concentration)
- C_{min} (minimum observed concentration)
- C_{trough} (Concentration before next dose)
- C_{aver} (average concentration in a 12 or 24 h dose interval)
- T_{max} (time to maximum observed concentration)
- T_{1/2} (terminal half-life)
- CL/F (apparent total clearance)
- V/F (apparent volume of distribution)
- R_{acc} (accumulation ratio for C_{max} and AUC in a 12 or 24 h dose interval)

Additional PK parameters may be determined, such as:

- λ_z (elimination rate constant)
- T_{lag} (Delay between the time of dosing and the time of appearance of plasma concentration)
- AUC_{tau} (the area under the concentration-time curve in a dosing interval)

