Statistical Analysis Plan

CX842A2107

Version 2.0, 04-Oct-2023

- 3. Confirmation of menopause. Only in questionable cases at the discretion of the Investigator.
- 4. Additional random alcohol and drug tests can be performed at subsequent visits at the discretion of the Investigator.
- 5. Resting systolic and diastolic blood pressure, pulse and body temperature. Blood pressure and pulse should be measured with the subject in a supine position, after 10 minutes of rest.
- 6. Randomization will take place after confirmation of all eligibility criteria evaluated at the screening visit and prior to the start of Visit 2.

- 9. The subjects will administer linaprazan glurate at home from Day 3 to Day 13.
- 10. Baseline symptoms will be recorded from the signing of the informed consent form (ICF) up until first dose on Day 1.
- 11. AEs will be recorded from (first) dosing on Day 1 up until the follow-up visit (Visit 8), or early withdrawal.

Statistical Analysis Plan

CX842A2107

Version 2.0, 04-Oct-2023

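### Does defining the accumulation ratio as last dose over first dose, with no day or time of day, leave R_acc open to a wrong calculation?

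*SAP*

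**What the plan says.** Section 5.6 gives the formula "R_{acc} AUC = AUC_{tau} last dose / AUC_{tau} first dose" and the same form for C_max. The parameter list in section 4.6.1 adds only the length of the interval: "accumulation ratio for C_{max} and AUC in a 12 or 24 h dose interval". Section 2.5 lists R_acc among the additional secondary PK parameters, and section 5.2.2 has it summarised descriptively.

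On dosing occasions, every dose group in section 3.1 is treated for 14 days. Appendix Table 1 puts Visit 5 on Days 14 to 15 and Visit 6 on Day 16, and its footnote 9 says: "The subjects will administer linaprazan glurate at home from Day 3 to Day 13". Section 5.4.6 says "During residential visits at the clinic (visits 2, 5 and 7), IMP will be administered at the clinic under medical supervision" and also "At visit 5 (day 14) to the clinic, subjects will be asked to return any unused study drugs and all empty containers". Section 3.3 notes that "The randomization list will contain subject number, block, gender, drug holiday period, and dose group". By contrast, the mean-pH summaries in section 5.7 name both the days (1 and 14) and the reference dose (morning for BID, evening for once daily, QD).

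**The concern.** The pH section fixes day and reference dose; the R_acc formula fixes neither. Two readings could then go astray.

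- **Visit 7 as the last dose.** Drug is given at Visit 7, which is numbered after Visit 6 (Day 16). Leftover drug is handed back on Day 14, and the randomization list carries a drug holiday variable. If Visit 7 follows a drug-free gap, a ratio of that dose to the first would sit near 1 whatever accumulation had occurred by Day 14.
- **Evening over morning in the BID groups.** If the last dose is the final one of the 14-day course, a BID subject's numerator could be a Day 14 evening interval and the denominator a Day 1 morning one. Any time-of-day or meal effect on exposure would be counted as accumulation. QD subjects, dosed in the evening on both days, would not be affected, so a QD-to-BID comparison could be blurred.

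At stake is the descriptive summary of one secondary parameter, for two analytes.

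**Working it through.** The SAP states no value for R_acc, half-life or time-of-day effect, so there is no figure to reproduce. The text settles the likely reading; the arithmetic shows only how much the other readings could matter under assumed inputs.

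**1. Which dose is meant.** R_acc sits in section 4.6.1 under primary and secondary analyses. Those serve the objective in section 2.1 and the endpoints in section 2.4, which concern single and repeated administration. The study title in section 1 specifies 14 days of repeated dosing, as does every group in section 3.1. In that scope the first and last doses are those of the 14-day course. The exploratory sections (2.3, 2.6 and the exploratory part of 4.6.1) are blank, and Visit 7 has no readable column in Appendix Table 1. Its day, its PK sampling and its link to the drug holiday are unknown. The ECG text in section 4.5.5, "at 24 hours post IMP-administration during visits 1, 2, 5 and 7", is weak evidence about Visit 7, because it also lists Visit 1, the screening visit, where Table 1 shows no study drug.

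**2. Model.** One compartment, linear kinetics, superposition. Assumed half-life T is 3 to 12 h, and r = 2^(−tau/T).

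*Like-for-like, Day 14 over Day 1:* R_acc ≈ 1/(1 − r).
- BID, tau = 12 h: T = 3 h gives r = 0.0625 and 1.07; T = 12 h gives r = 0.5 and 2.00.
- QD, tau = 24 h: T = 3 h gives r = 0.0039 and 1.00; T = 12 h gives r = 0.25 and 1.33.

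*Visit 7 after a gap G:* 1 + 2^(−G/T)/(1 − r), with r as above for the preceding course. G is assumed; 48 h is about the least the visible schedule allows, since Visit 6 is on Day 16.
- T = 12 h, G = 48 h: BID 1 + 0.0625 × 2.00 = 1.125; QD 1 + 0.0625 × 1.333 = 1.083.
- T = 12 h, G = 96 h: BID 1.008; QD 1.005.

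Such a ratio would not measure accumulation, which is a further reason to doubt that it is intended.

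**3. Evening over morning, BID.** Let f be the exposure of an evening dose relative to a morning dose (assumed 0.8 to 1.25).
- Morning/morning = (1 + f·r)/(1 − r²)
- Evening/morning = (f + r)/(1 − r²)

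| T | f | morning/morning | evening/morning |
|---|---|---|---|
| 3 h | 0.8 | 1.05 | 0.87 |
| 3 h | 1.25 | 1.08 | 1.32 |
| 6 h | 0.8 | 1.28 | 1.12 |
| 6 h | 1 | 1.33 | 1.33 |
| 6 h | 1.25 | 1.40 | 1.60 |
| 12 h | 0.8 | 1.87 | 1.73 |
| 12 h | 1.25 | 2.17 | 2.33 |

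Example, T = 6 h and f = 0.8: r = 0.25 and 1 − r² = 0.9375, so (0.8 + 0.25)/0.9375 = 1.12 against (1 + 0.2)/0.9375 = 1.28. A wider assumption, f from 0.7 to 1.3 at T = 4 h, gives 0.84 against 1.10 and 1.45 against 1.18, or about −24% to +23%. At f = 1 the two formulas are identical for every T, so there is no bias.

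**4. What else is reported.** AUC over 0–12 h, 12–24 h and 0–24 h after single and repeated dosing are primary endpoints where applicable (section 2.4). Section 5.2.2 lists parameters by subject, exports them at full precision and lists every individual concentration. If both BID intervals are profiled, a morning/morning AUC ratio can be formed from these outputs. If only the morning interval is profiled, the mismatch cannot arise for AUC.

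**The case for a change.** The strongest opposing case is that section 5.6 is where the SAP undertakes to describe its calculations in detail, that the authors did name day and reference dose for pH, and that one sentence would settle the matter before the analysis of an open-label study. The visible text does say that drug is given at Visit 7, so a literal reader has some basis for that reading. The list of both 0–12 h and 12–24 h AUCs means that an analyst might have both BID intervals to choose from.

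Part of this stands: the formula is incomplete as written, and the wording does not exclude an evening-over-morning pairing. What does not stand is the step from incomplete to wrong. The Visit 7 reading goes against the 14-day scope of the parameter and fills in a schedule that cannot be seen. The BID mismatch needs a Day 14 evening dose, a profiled evening interval and a diurnal difference in exposure. The first is an inference from BID dosing for 14 days, the second depends on protocol section 11.3.1, which is not at hand, and nothing in the SAP supports the third.

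**Conclusion.** No change to the plan is called for. The day and interval for R_acc are unstated, but the parameter's place in the SAP leads to Day 14 over Day 1 on matching profiled intervals, which is how a pharmacokineticist would ordinarily calculate it. No wrong result is shown. On that reading, with an assumed half-life of 3 to 12 h, the AUC ratio would be 1.07 to 2.00 for BID and 1.00 to 1.33 for QD. The BID mismatch could shift it by up to about a quarter under a strong assumed time-of-day effect, and by nothing if evening and morning exposures are equal. All these figures rest on linear one-compartment kinetics and on inputs the SAP does not supply. R_acc is a descriptive secondary parameter with no test or decision rule attached. The primary PK and pH endpoints do not depend on it, and the AUCs and concentrations behind it are reported in their own right. A colleague who wished to name the day and interval when preparing the tables could do so without altering the analysis.
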